12.1. Determination of Sample Size

Approximately 240 subjects will be randomized to 1 of 4 double-blind treatment regimens to evaluate the primary endpoint. Subjects will be randomized to placebo, 50 mg LY3074828 exposure-based dosing, 200 mg LY3074828 exposure-based dosing, or the 600-mg LY3074828 fixed-dose treatment group in a 1:1:1:1 ratio (60 subjects per arm). The randomized subjects will comprise approximately one-third biologic-naïve subjects (~20 per arm) and approximately two-thirds previous biologic therapy subjects (received treatment with 1 or more agents such as TNF antagonists, vedolizumab, or experimental UC biologics) (~40 per arm).

Assuming LY3074828 and placebo clinical remission rates of 30% and 7.5% respectively (a difference of 22.5%) and given 60 subjects per treatment arm, each pairwise comparison testing the superiority of LY3074828 to placebo will have 89% power via chi-square test with a two-sided 0.05 significance level.

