12.2.6. Efficacy and Health Outcome Analyses

12.2.6.1. Primary Analyses

Rates of clinical remission at Week 12, as defined in Section 10.1.1, will be analyzed.

Subjects who do not achieve clinical remission or who do not reach the Week 12 assessment will be considered to be nonremitters.

The rates of clinical remission and nonremission will be summarized by dose level and previous biologic use (yes/no). The differences between each treatment arm and placebo will be tested separately via a logistic regression model that controls for previous biologic use.

The primary analysis will be based on the ITT population.

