The primary analysis of categorical (binary) efficacy and health outcome variables will use a logistic regression analysis with treatment, geographic region, and prior biologic experience (prior biologic experience vs prior biologic naïve), and visit (when appropriate) in the model. The odds ratio, the corresponding 95% CIs and p-value, as well as the treatment differences (where appropriate) and the corresponding 95% CIs, will be reported. Secondary analysis will be conducted using an exact Cochran-Mantel-Haenszel test that stratifies by (i.e., controls for) previous biologic use. A Fisher's exact test may be utilized if necessary.

The primary analyses for all continuous efficacy and health outcome variables will be based on the MMRM analysis method. The MMRM analyses will be conducted using a restricted maximum likelihood (REML)-based repeated measures approach. When MMRM is used, the model will include treatment, visit, geographic region, prior biologic experience (prior biologic

experience vs prior biologic naïve), treatment-by-visit interaction, as well as the continuous, fixed covariates of baseline value and baseline value-by-visit interaction. The covariance structure to model the within-patient errors will be unstructured. If the unstructured covariance matrix results in a lack of convergence, the heterogeneous Toeplitz covariance structure, followed by the heterogeneous autoregressive covariance structure, followed by the compound symmetry structure will be used. The first structure to yield convergence will be used for inference. The Newton-Raphson with ridging optimization technique will be used to aid with convergence. The Kenward-Roger approximation will be used to estimate the denominator degrees of freedom and adjust standard errors. Type III tests for the LS means will be used for the statistical comparison; the 95% CI will also be reported. Treatment group comparisons with placebo at Week 12 (Visit 7) and all other appropriate time points will be tested.

Secondary treatment comparisons of continuous efficacy variables at Week 12 and 52 will be made using ANCOVA with treatment, geographic region, prior biologic experience (prior biologic experience vs prior biologic naïve), and baseline value in the model. Type III sums of squares for the least-squares (LS) means will be used for the statistical comparison; the 95% confidence interval will also be reported.

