6.11. Efficacy Analyses

6.11.1. Primary Outcome and Methodology

Rate of clinical remission at Week 12 is the primary efficacy outcome for this study and will be analyzed using the ITT population.

The primary objective of this study is to test the hypothesis that treatment with LY3074828 is superior to placebo in inducing clinical remission at Week 12 in patients with moderate to severe ulcerative colitis (UC)

Clinical remission is defined as achieving a rectal bleeding Mayo subscore of 0, stool frequency Mayo subscore of 0 or 1 (with 1 point decrease from baseline) and Mayo endoscopic subscore of 0 or 1.

The rates of clinical remission and non-remission will be summarized by treatment group and by the stratification factor, previous biologic use (yes/no). See section 6.1 for details on the methods to be used to test the differences between each active treatment arm and placebo.

Ninety five percent confidence interval for the difference in proportions (LY arm – placebo) for each pairwise comparison will be obtained. If the lower limit of the 95% confidence limit is greater than zero, then that arm will be considered to be superior to placebo.

A multiple testing procedure will be utilized for the primary outcome and is detailed in section 6.6.

See section 6.4.1 for details on NRI.

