6.15.1. Efficacy Subgroup Analysis

Subgroup analyses will be conducted for the following efficacy assessments:

- Clinical Remission at 12 weeks

Subgroups to be evaluated include the following:

- Patient Demographic Subgroups:
 - Gender: female or male
 - Age group: < 65 years, ≥65 years
 - Race: American Indian/Alaska Native, Asian, Black/African American, Native Hawaiian/Other Pacific Islanders, White, or Multiple Races
 - Ethnicity: Hispanic/Latino, Non-Hispanic/Non-Latino
 - Weight: <100 kg or ≥100 kg
 - Weight: <80 kg, ≥80 and <100 kg, or ≥ 100 kg

- Body mass index (BMI, kg/m^2) category (underweight ($<18.5 \text{ kg/m}^2$); normal (≥ 18.5 and $<25 \text{ kg/m}^2$); overweight (≥ 25 and $<30 \text{ kg/m}^2$); obese (≥ 30 and $<40 \text{ kg/m}^2$); or extreme obese ($\geq 40 \text{ kg/m}^2$))
- Geographic Region Subgroups:
 - Geographic region: North America, Asia (Japan) and Rest of World (incl. EU and Australia, NZ)
- Prior/Concomitant UC Therapy:
 - Prior Biologic therapy vs Biologic Naïve
 - Concomitant UC Baseline Medication:
 - Corticosteroid current use (concomitant use of any medications with ATC codes A07EA, H02AB, A01AC) vs none
 - 5 ASAs current use (concomitant use of any medications with ATC code A07EC) vs none
 - Thiopurines current use (e.g. azathioprine; concomitant use of any medications with ATC code L01BB, LO4AX (where Preferred name= “AZATHIOPRINE”)) vs none
 - More than one of the above
- Baseline Severity Groups:
 - Mayo score at baseline (6-8, 9-12)
 - CRP: 6 mg/L, $>6 \text{ mg/L}$
- Other Baseline Patient Characteristics Subgroups:
 - Smoking status at baseline: yes or no
- Therapeutic Drug Monitoring Subgroup
 - TDM adjustment status: yes or no

For Week 12 Clinical Remission analyses, a logistic regression model with treatment, subgroup, and the interaction of treatment-by-subgroup included as factors will be used. The treatment-by-subgroup interaction will be tested at the significance level of 0.10. Treatment group differences will be evaluated within each category of the subgroup using Fisher’s exact test, regardless of whether the interaction is statistically significant. Missing data will be imputed using NRI, as described in Section 6.4.1. If any group within the subgroup (for example, yes, no) is less than 10% of the total population, only descriptive statistics will be provided for that subgroup (that is, no inferential testing).

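### The binary Mayo endpoints are modelled without the baseline Mayo score: a valid analysis that passes up a small, cheap gain in efficiency

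*SAP*

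**What the plan says.** **Binary endpoints.** SAP 6.1 specifies this model: "logistic regression analysis with treatment, geographic region, and prior biologic experience (prior biologic experience vs prior biologic naïve), and visit (when appropriate) in the model". This covers clinical remission, clinical response and endoscopic remission. The supporting exact CMH test in SAP 6.1 stratifies by prior biologic use only. The protocol's own models (12.2.6.1 and 12.2.6.2) adjust for prior biologic use only. None of these has a baseline Mayo term.

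**Continuous endpoints.** The MMRM in the same section has the design factors "as well as the continuous, fixed covariates of baseline value and baseline value-by-visit interaction", and the ANCOVA also has the baseline value.

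**SF-36.** In SAP 6.12.1.1 the ANCOVA of change in the component scores includes the baseline score. The logistic model for MCID responders on those same scores does not.

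**Availability.** A Mayo score of 6 to 12 is an entry criterion (Protocol 8.1, criterion 5), and a full Mayo score is scheduled at Visit 2 (Protocol Attachment 1). Endoscopy is read centrally for the endpoints (Protocol 10.1.4).

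**Where baseline Mayo does appear.** SAP 6.15.1 lists "Mayo score at baseline (6-8, 9-12") as a severity subgroup for Week 12 remission. Baseline stool frequency also enters the remission definition, which requires "stool frequency Mayo subscore of 0 or 1 (with 1 point decrease from baseline").

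The documents give no reason for leaving baseline Mayo out of the main binary models.

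**The concern.** A baseline measurement of the outcome is often a useful covariate, and here it costs nothing to obtain. The sponsor already treats baseline Mayo as a marker of severity, and the endpoints are defined partly by change from baseline. Randomisation is stratified by prior biologic use only (SAP 6.3), so severity can differ between arms of 60 by chance, and the main binary models would not correct for that. Region is in the model although it is not a stratification factor (SAP 6.5), so the covariate list was not confined to the randomisation factors.

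At stake are some power for the three primary comparisons, some precision in the risk difference, and protection against chance imbalance in severity. The subgroup model does not supply these. It tests an interaction and is followed by Fisher tests within categories, so it gives no severity-adjusted overall effect.

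**Working it through.** **1. Reproduce the plan's figure.** Protocol 12.1 gives 30% vs 7.5%, 60 per arm, two-sided 0.05, and says "each pairwise comparison testing the superiority of LY3074828 to placebo will have 89% power via chi-square test with a two-sided 0.05 significance level".

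- Pooled rate: (0.30 + 0.075)/2 = 0.1875.
- SE under no difference: √(2 × 0.1875 × 0.8125/60) = 0.0713.
- SE under the alternative: √((0.075 × 0.925 + 0.30 × 0.70)/60) = 0.0682.
- Power: Φ((0.225 − 1.96 × 0.0713)/0.0682) = Φ(1.25) = 89.4%.

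The stated 89% is right and assumes no covariate gain.

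**2. Events available.** 60 × 0.075 = 4.5 placebo remitters and 60 × 0.30 = 18 on active, so 22.5 per pairwise comparison.

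**3. Effect of adding baseline Mayo to the remission model.** The documents give no prognostic strength, so a range was simulated: 10,000 trials per setting, 60 vs 60, with marginal rates held at 30% and 7.5%. Both models contained treatment and prior biologic use; the second added a linear baseline Mayo term. Assumptions that are not in the documents:

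- full Mayo score of 6 to 12 with mean 8.7 and SD 1.6, standing in for the 9-point score;
- odds ratio 0.5 for prior biologic use;
- odds ratio per Mayo point from 1.0 to 0.6;
- region left out of both models.

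The SAP does not name the test, so likelihood-ratio (LR) and Wald results are both shown (without → with baseline).

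| Odds ratio per Mayo point | LR power, % | Wald power, % | Variance ratio, standardised risk difference | Median SE of log odds ratio |
|---|---|---|---|---|
| 1.0 | 92.3 → 92.1 | 90.1 → 89.9 | 1.01 | 0.588 → 0.592 |
| 0.9 | 92.5 → 92.2 | 90.1 → 90.0 | 1.01 | 0.587 → 0.592 |
| 0.8 | 92.2 → 92.4 | 89.9 → 90.4 | 0.99 | 0.588 → 0.597 |
| 0.7 | 92.1 → 93.1 | 89.7 → 91.1 | 0.96 | 0.588 → 0.605 |
| 0.6 | 92.3 → 94.0 | 90.2 → 91.9 | 0.93 | 0.587 → 0.619 |

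The power change runs from −0.3 to +1.7 points. At 25% vs 7.5% it runs from −0.5 point (LR, odds ratio 0.9) to +2.9 points (Wald, odds ratio 0.6). With 7.5% in both arms, rejection rates barely move: LR 6.2–6.9% without and 6.3–6.9% with; Wald 1.5–1.8% without and 1.8–2.3% with.

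The standard error of the log odds ratio rises on adjustment in every row. Any benefit therefore shows in power and in the standardised risk difference, not in a narrower odds-ratio interval.

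**4. Chance imbalance.** The difference between two arm means of baseline has standard error √(2/60) = 0.18 SD, so a gap above 1.96 × 0.18 = 0.36 SD arises in about 5% of comparisons. At an assumed odds ratio of 0.7 per point and SD 1.6, a gap of that size shifts the log odds ratio by 0.36 × 1.6 × |ln 0.7| ≈ 0.2. The planned effect is ln[(0.30/0.70)/(0.075/0.925)] = 1.67.

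No simulation was run for clinical response, endoscopic remission or the SF-36 MCID. For those the argument is one of consistency, not of calculated size.

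**The case against.** The case for leaving the model alone is strong in several respects.

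- *No error is shown.* The stratification factor is in the model and the power claim reproduces. This stands.
- *Prognostic strength is unknown.* Entry restricts Mayo to 6–12, and neither direction nor linearity is evident. Higher scorers have further to fall for remission but more room to meet the response criteria. This stands, and is why the gain is given as a range that includes a small loss.
- *Events are few.* With about 22.5 per comparison, and with region (three levels) and prior biologic use already in the model, the list must stay short. This stands; it limits the change to one linear term.
- *Missing baseline values could cost more than is gained.* Dropping 2 or 3 patients per arm takes the step 1 power to 88.4% (n = 58) or 87.8% (n = 57). This stands unless a missing-value rule is written.
- *Timing.* The SAP's Revision History records approval of version 3.0 after unblinding. Replacing the primary model then would be a post hoc change to the confirmatory test, and would move it further from Protocol 12.2.6.1. This stands.

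A reader might also infer more than the documents support:

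- *A large loss of power.* Applying the linear-model factor 1 − ρ² with ρ = 0.5 makes the effective sample 60/0.75 = 80 per arm and power 96.1%, an apparent gain of 6.6 points. No ρ is given, and the factor is a linear-model result. At a 7.5% placebo rate, the correlation between a normal covariate and the outcome cannot exceed φ(1.44)/√(0.075 × 0.925) = 0.1415/0.2634 = 0.54, even with perfect prediction, so 0.5 is not a realistic default.
- *Every continuous measure is adjusted and no binary model is.* Neither holds: histology scores are compared by an unpaired t-test (SAP 6.14.9), and the SAP 6.15.1 subgroup model does contain baseline Mayo.

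**Conclusion.** The point holds as a missed efficiency and a minor inconsistency. The planned analysis is valid and the 89% power stands.

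For Week 12 remission, one baseline Mayo term would gain about 0 to 2 power points per comparison and lower the variance of the standardised risk difference by 0 to 7%. If baseline is barely prognostic, up to about 0.5 point could be lost. This rests on the assumed odds ratios, Mayo distribution and prior-biologic effect in step 3, none of which is in the documents. Correction of chance severity imbalance is a further benefit whose size also depends on prognostic strength.

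The other binary endpoints share the omission, but no size is claimed for them. The point is optional, and worth taking up because it is cheap.

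**What to change.** In SAP 6.1, add one continuous, linear baseline 9-point Mayo term (rectal bleeding + stool frequency + centrally read endoscopy) to the logistic models for clinical remission, clinical response and endoscopic remission. In SAP 6.12.1.1, add the corresponding baseline component score to the SF-36 MCID model. Keep prior biologic use and region, and add no further terms.

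Report the standardised (marginal) risk difference with its 95% confidence interval beside the odds ratio; SAP 6.1 and 6.11.1 already plan a difference in proportions. State a simple rule for a missing baseline value, such as the mean over all randomised patients regardless of arm, so that no ITT patient is dropped. If the sponsor prefers to leave the term out, one sentence giving the reason would do.

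A change made at SAP version 3.0 or later should be a labelled supportive analysis, with the planned model kept as primary.

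**Cost:** a few lines of SAP text and one model term, with no new data. The odds ratio becomes conditional on baseline severity and its standard error rises, so it should not be read as the measure of gained precision.

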6.2. Analysis Populations

The patient populations to be analyzed for this study are defined in the table presented below:

Table 2 Analysis Populations

Population	Definition
Screening	All patients who signed informed consent and participated in the screening period (Visit 1). This population will be used for the presentation of patient disposition.
Intent-to-Treat (ITT) Population	Efficacy and health outcome analyses will be conducted on the intent-to-treat population (ITT). The ITT population is defined as all randomized patients, even if the patient does not take the assigned treatment, does not receive the correct treatment, or otherwise does not follow the protocol. Patients will be analyzed according to the treatment to which they were assigned.
Safety Population	Safety analyses will be conducted on the Safety Population, defined as all randomized patients who receive at least one dose of study treatment. Patients will be analyzed according to the treatment to which they were assigned.

Induction Responders	A subset of the ITT population and will include those patients who are re-randomized to one of the two maintenance dosing period LY arms.
All enrolled in Extension Period	A subset of the ITT population and will include only the patients who participated in the Extension Period.

Analyses of the maintenance dosing period and the extension periods will be based on the corresponding enrolled population as described in the table above.

The Schedule of Events outlined in the protocol (attachment 1) specifies the allowable windows for assessments. A sensitivity analysis of the primary analysis may be conducted to investigate the exclusion of patients /assessments deemed to be major deviations from the protocol.

A Per-Protocol population may be evaluated in this study and patients to be excluded from that population will be identified through protocol deviations. All protocol exemptions and violations will be listed as described in section 9.10 of the protocol.

All statistical analyses will be performed using SAS software Version 9.2 (or a higher version). Visualizations tools such as Spotfire may also be used for dynamic displays.

6.3. Adjustments for Covariates

The randomization at the beginning of the Induction Period is stratified by previous biologic therapy: previous exposure to biologic therapy for treatment of UC, biologic naïve to biologic therapy for treatment of UC. Unless otherwise specified, all efficacy and health outcome analyses will include the stratification factors in the model.

The re-randomization at the beginning of the Maintenance Period of patients who took LY3074828 during the Induction Period and were responders at Week 12 (Visit 7) is stratified by the Week 12 level of clinical response: Clinical Remission or Clinical Response. Unless otherwise specified, all efficacy and health outcomes analyses using the Maintenance Dosing Period Primary population will include the re-randomization factor of Week 12 level of response in the model.

Unless otherwise specified, analyses will be performed utilizing the methodology and covariates described in section 6.1.

6.4. Handling of Dropouts or Missing Data

Details of the handling of dropouts or missing data are presented in the following sections.

Details of the procedure for handling missing data for the IBDQ are provided in Appendix B.

Details of handling missing partial end dates for prior medications for important programmable deviations are provided in section 6.16 Protocol Violations.

6.4.1. Non-Responder Imputation (NRI)

The primary outcome is the proportion of patients with clinical remission at 12 weeks. For this and other categorical efficacy endpoints (for example, clinical remission (week 52), clinical response (week 12, 52), and endoscopic remission (week 12, 52)), non-responder imputation (NRI) will be used for missing clinical assessment values. Specifically, all patients who discontinue from the study at any time prior to week 12 for any reason or fail to have an adequate week 12 efficacy assessment will be considered a non-responder at week 12. Patients who discontinue from the study for any reason at any time prior to week 52 after having enrolled into the Maintenance Period or fail to have an adequate week 52 efficacy assessment, will be considered a non-responder at week 52.

The NRI may be applied at any time point specified for analysis.

6.4.2. Last Observation Carried Forward

An LOCF analysis will be performed on PGI-I.

This is both a sensitivity analysis, and an analysis for regulatory agencies that prefer this approach. This approach is identical to the mBOCF approach, with one exception: for patients discontinuing investigational product due to an AE, the last non-missing post-baseline observation before discontinuation will be carried forward to the corresponding endpoint for evaluation. Randomized patients without at least one post-baseline observation will not be included for evaluation.

6.4.3. Modified Baseline Observation Carried Forward

An mBOCF analysis will be performed on key continuous efficacy and the PGI-S and the IBDQ.

This is both a sensitivity analysis, and an analysis for regulatory agencies that prefer this approach. For patients discontinuing investigational product due to an AE, the baseline observation will be carried forward to the corresponding primary endpoint for evaluation. For patients discontinuing investigational product for any other reason, the last non-missing post-baseline observation before discontinuation will be carried forward to the corresponding primary endpoint for evaluation. Randomized patients without at least one post-baseline observation will not be included for evaluation with the exception of patients discontinuing study treatment due to an AE.

6.4.4. Missing Data Imputation for Adverse Event, Concomitant Medication Dates, and Laboratory Values

If a medication date or AE date is completely or partially missing, the following imputation rules should be utilized in the analysis unless otherwise stated:

- For the start date:
 - If year, month, and day are missing then use the earlier of the patient's first visit date or the consent date.
 - If either month or month and day are missing then use January 1.

- If only day is missing, impute the first day of the month.
- For the start time:
 - Impute as 23:59.
- For the end date:
 - If year, month, and day are missing then use the patient's last visit date.
 - If either month or month and day are missing then use December 31.
 - If only day is missing then use the last day of the month.
 - The imputed date will not be beyond the patient's last visit date.

If there is any doubt for the start and end date/times for AEs, the event will be flagged as treatment-emergent. For medications, the medication will be flagged as concomitant.

Laboratory parameters will be summarized based on the available data at each time point and no imputation is proposed in this document.

